1. SYNOPSIS OF THE CLINICAL INVESTIGATION

Sponsor	Element Science, Inc.
Name of Product	Jewel Electrophysiology (EP) Lab System
Title	Jewel Electrophysiology (EP) Lab Study
Study Design	
This single center, prospective, single arm study will be conducted in the European Union. The sample size for the study is a maximum of 24 subjects. The study design will allow for continuous enrollment of eligible subjects until the sample size is met for the treatment analysis per the statistical analysis plan.
 
The study will enroll subjects who are scheduled for a standard EP procedure where life-threatening VT or VF may spontaneously occur or may be induced.

Primary Objective	The primary objective of this study is to demonstrate safety and clinical effectiveness of the Jewel EP Lab System. The Jewel EP Lab System will be used to deliver a single transthoracic defibrillation shock to terminate life-threatening VT or VF.
Primary Endpoint	Primary Endpoint: The primary effectiveness endpoint will evaluate the percent of successful terminations of life-threatening VT or VF in subjects who are treated with the Jewel EP Lab System.
Safety Endpoint	Safety Endpoint: Descriptive statistics of safety outcomes will be reported to ensure that device safety performance is clinically meaningful. All adverse events (AEs) and serious adverse events (SAEs) during the acute procedure will be tabulated and presented along with the duration, severity, and relatedness to the Jewel EP Lab System. The proportion of subjects experiencing an AE or SAE will also be presented. No formal safety analyses will be performed due to the fact that the sample size does not allow for a powered safety endpoint.
Study Participants	
Subjects must meet the following inclusion/exclusion criteria to be eligible for the study:
 
Inclusion Criteria
 
 1. Subjects of both genders of at least 18 years of age. 2. Subjects who are scheduled for a standard EP clinical procedure where fast VT or VF may spontaneously occur or may be induced. 
Exclusion Criteria
 
 1. Subjects who may require sterile access to the right upper pectoral or lower left torso regions during the planned EP procedure. 2. Subjects who have taken amiodarone in the past 3 months. 3. Subjects with an existing unipolar pacemaker. 4. Subjects who exhibit a left ventricular ejection fraction (LVEF) less than 20% (as assessed by techniques such as echocardiography,

	
magnetic resonance imaging, or radionuclide angiography) within the last 6 months.
 
 5. Subjects who have been diagnosed with heart failure (Class IV) or experienced an acute heart failure exacerbation within the previous 30 days. 6. Subjects who exhibit unstable angina. 7. Subjects with atrial fibrillation with contraindication to anticoagulation or improper anticoagulation management. 8. Subjects who are participating in an investigational study of a drug, biologic, or device not currently approved for marketing. 9. Subjects who are allergic to or have had a known adverse reaction to medical adhesives. 10. Subjects who have active skin breakdown, erythema, or other signs of infection in the pectoral or torso regions where the study device is applied. 11. Subjects with a lower abdomen circumference of less than 68.5 cm or greater than 142 cm. 12. Females who are pregnant or breastfeeding, or planning to be pregnant in the next 12 months. 13. Subjects who cannot provide or have diminished capacity to provide informed consent. 14. Any condition that an Investigator believes would interfere with the intent of the study or is not in the best interest of the patient. 15. Any patient that according to the Declaration of Helsinki is unsuitable for enrollment. 
Note: Subjects with an active implanted device, such as a pacemaker, ICD, or a subcutaneous-ICD, are not excluded in the eligibility criteria, but the Investigator may choose to screen out subjects where the active device or clinical procedure may interfere with the intent of the study.

Study Device	
The Jewel System is patch-wearable cardioverter defibrillator (P-WCD) applied directly to a patient's torso in an anterior-apical monitoring vector.
 
The Jewel EP Lab System consists of a Jewel (ES-1, ES-2) System modified with the addition of a Controller Box to allow the operator to manually charge and manually administer a defibrillation shock. All other elements of the Adhesive Electrode Patches are identical to the Jewel (ES-1, ES-2) System.

Procedure	
The study device is intended to be used in conjunction with a standard EP clinical procedure. The Jewel EP Lab System will be used to terminate the first spontaneous or induced life-threatening episode of VT or VF. As an added safety precaution, rescue defibrillator pads will be placed on the subject in the anterior-posterior position and connected to a rescue defibrillator.

TABLE OF CONTENTS

1. SYNOPSIS OF THE CLINICAL INVESTIGATION	2
2. LIST OF ABBREVIATIONS.....	5
3. INTRODUCTION	6
3.1. SUDDEN CARDIAC DEATH.....	6
3.2. DEVICE DESCRIPTION: JEWEL SYSTEM.....	6
3.3. DEVICE DESCRIPTION: JEWEL EP LAB SYSTEM	10
3.4. PRIOR CLINICAL EXPERIENCE WITH THE JEWEL AND JEWEL EP LAB SYSTEMS	10
3.5. RISKS AND BENEFITS OF THE JEWEL EP LAB SYSTEM.....	10
4. STUDY OBJECTIVE	11
5. STUDY PURPOSE	11
6. STUDY DESIGN	13
6.1. PRIMARY EFFICACY ENDPOINT.....	13
6.2. PRIMARY SAFETY ENDPOINT	13
7. STUDY POPULATION	14
7.1. PATIENT INCLUSION/EXCLUSION CRITERIA.....	14
8. STUDY ACTIVITIES	15
8.1. SUBJECT ENROLLMENT	15
8.2. STUDY PROCEDURE.....	16
8.3. FOLLOW-UP.....	18
9. SUBJECT REMOVAL FROM STUDY	18
10. ASSESSMENT OF SAFETY.....	19
10.1. SAFETY DEFINITIONS	19
10.2. REPORTING OF ADVERSE EVENTS.....	20
10.3. FOLLOW-UP OF PATIENTS AFTER ADVERSE EVENTS / SERIOUS ADVERSE EVENTS	21
11. STATISTICS.....	22
11.1. STATISTICAL ANALYSIS AND SAMPLE SIZE RATIONALE	22
12. ADMINISTRATIVE CONSIDERATIONS	25
12.1. INVESTIGATORS AND STUDY ADMINISTRATIVE STRUCTURE	25
12.2. INDEPENDENT ETHICS COMMITTEE (IEC) APPROVAL	25
12.3. ETHICAL CONDUCT OF THE STUDY.....	25
12.4. ADHERENCE TO PROTOCOL.....	25
12.5. PATIENT CONFIDENTIALITY	25
13. STUDY MONITORING	26
13.1. TRAINING.....	26
13.2. ACCOUNTABILITY OF THE JEWEL EP LAB SYSTEM COMPONENTS	26
13.3. CASE REPORT FORMS AND STUDY RECORDS	26
13.4. PROTOCOL DEVIATIONS	27
13.5. AMENDMENTS	27
13.6. ACCESS TO SOURCE DOCUMENTATION	27
13.7. RETENTION OF DATA	28
14. SUPPLEMENTS	29
14.1. INVESTIGATOR'S AGREEMENT	29

2. LIST OF ABBREVIATIONS

ADE	Adverse Device Effect
AE	Adverse Event
AED	Automated External Defibrillator
CABG	Coronary Artery Bypass Graft
CMS	Centers for Medicare and Medicaid Services
CRF	Case Report Form
DD	Device Deficiency
DME	Durable Medical Equipment
ECG	Electrocardiogram
EP	Electrophysiology
EU	European Union
FDA	Food and Drug Administration
ICD	Implantable Cardioverter Defibrillator
IEC	Independent Ethics Committee
ISO	International Organization for Standardization
ITT	Intent to Treat
LVEF	Left Ventricular Ejection Fraction
MI	Myocardial Infarction
NYHA	New York Heart Association
PCI	Percutaneous Coronary Intervention
PIC	Patient Informed Consent
P-WCD	Patch-Wearable Cardioverter Defibrillator
RCT	Randomized Controlled Trial
SADE	Serious Adverse Device Effect
SAE	Serious Adverse Event
SCD	Sudden Cardiac Death
S-ICD	Subcutaneous Implantable Cardioverter Defibrillator
SOP	Standard Operating Procedure
TTI	Transthoracic Impedance
UADE	Unanticipated Adverse Device Effect
US	United States
VF	Ventricular Fibrillation
VT	Ventricular Tachycardia
WCD	Wearable Cardioverter Defibrillator

3. INTRODUCTION

3.1. SUDDEN CARDIAC DEATH

Sudden Cardiac Death (SCD) is sudden, unexpected death caused by the abrupt loss of heart function, and is one of the largest causes of natural death in Europe, leading to 275,000 adult deaths each year.¹ SCD is most often caused by abnormal heart rhythms, called arrhythmias, which prevent the heart from adequately pumping blood to the body. Ventricular Fibrillation (VF) is an erratic, disorganized firing of impulses from the ventricles and is the most common life-threatening arrhythmia.² Ventricular Tachycardia (VT) occurs when the heart's ventricles rapidly contract due to improper electrical activity and can also be potentially life threatening.

While the Implantable Cardioverter Defibrillator (ICD) is typically implanted for long-term prevention of SCD in high-risk populations, there are temporary periods of time when ICD implantation is commonly deferred. Examples include the initial 40 days after myocardial infarction (MI), the initial 90 days after percutaneous coronary intervention (PCI) or coronary artery bypass grafting (CABG), or after ICD explantation. The Wearable Cardioverter Defibrillator (WCD) has become a viable option to treat temporary periods of elevated risk for SCD. Patients are typically prescribed to wear a WCD 24 hours a day, 7 days a week, for 40 to 90 days or longer, until a medical decision is made on whether to implant an ICD.³

3.2. DEVICE DESCRIPTION: JEWEL SYSTEM

Element Science, Inc. is developing the Jewel Patch Wearable Cardioverter Defibrillator (P-WCD) System (“Jewel System”) for patients who are at risk of SCD to improve the comfort and convenience of a WCD by focusing on developing a patient-centric design. The Jewel System continuously monitors a patient’s cardiac rhythm and, in the event that a patient experiences a life-threatening episode of VT (greater than ~200 beats per minute) or VF, delivers a therapeutic shock to convert a patient’s rhythm out of the detected VT or VF. The device used in this study is a modified version of the Jewel System.

The study includes both the ES-1 model and the ES-2 model of the Jewel System. *The ES-1 and ES-2 models, together referred to as the Jewel family, have identical functionality while incorporating device improvements and meeting Durable Medical Equipment (DME) requirements specified by the United States Centers for Medicare and Medicaid Services for reimbursement (Defibrillator Unit of the ES-2 model is now reusable).* The Jewel EP Lab System utilized in this study consists of a Jewel (ES-1, ES-2) modified with the addition of a Controller Box to allow the operator to manually administer a defibrillation shock. All other elements of the Adhesive Electrode Patches are identical to the Jewel (ES-1, ES-2) System.

¹ European Resuscitation Council Guidelines for Resuscitation 2010 Section 10. Resuscitation. 2010; 81: 1445-1451.

² “Sudden Cardiac Death (Sudden Cardiac Arrest) | Cleveland Clinic.” Sudden Cardiac Death (Sudden Cardiac Arrest) | Cleveland Clinic. Cleveland Clinic, 1 May 2015. Web. 08 Jan. 2016.

³ Chung MK, Szymkiewicz SJ, et. al. “Aggregate national experience with the wearable cardioverter-defibrillator: event rates, compliance, and survival”. J Am Coll Cardiol. 2010; 56: 194–203.

ES-1 Model of the Jewel EP Lab System (“Jewel”)

The ES-1 model of the Jewel System includes the following three components: Upper Adhesive Electrode Patch, Monitoring and Defibrillation Unit with Lower Adhesive Electrode Patch, and Connection Cable. A schematic of the system is shown in Figure 3.1 and a brief description of each component is outlined in Table 3.1.

Figure 3.1: Schematic of Jewel (ES-1) System Components

Table 3.1: ES-1 Model of the Jewel System Component Descriptions

Jewel System Component	Description
Upper Adhesive Electrode Patch	Conformable adhesive patch containing ECG electrodes and a defibrillation electrode.
Monitoring and Defibrillation Unit with Lower Adhesive Electrode Patch	Conformable adhesive patch containing ECG electrodes and a defibrillation electrode. All electronics are contained within the Monitoring and Defibrillation Unit, which is integrated with the Lower Adhesive Electrode Patch. Control Buttons are located on the exterior of the Monitoring and Defibrillation Unit.
Connection Cable	Multi-conductor cable assembly connecting the Upper Adhesive Electrode Patch to the Monitoring and Defibrillation Unit with Lower Adhesive Electrode Patch.

ES-2 Model of the Jewel EP Lab System (“Jewel”)

The ES-2 model of the Jewel System is composed of the following three components: disposable Upper Adhesive Electrode Patch, a reusable Monitoring and Defibrillation Unit (MDU) attached to a disposable Lower Adhesive Electrode Patch with permanently attached disposable Battery Unit, and the attached Connection Cable. A schematic of the ES-2 is shown in Figure 3.2 and a description is contained in Table 3.2.

Table 3.2: ES-2 Model of Jewel System Component Descriptions

Jewel System Component	Description
Upper Adhesive Electrode Patch	Conformable adhesive patch containing ECG electrodes and a defibrillation electrode.
Monitoring and Defibrillation Unit with Lower Adhesive Electrode Patch	Conformable adhesive patch containing ECG electrodes and a defibrillation electrode. All electronics are contained within the Monitoring and Defibrillation Unit, which is integrated with the Lower Adhesive Electrode Patch. Control Buttons are located on the exterior of the Monitoring and Defibrillation Unit.
Connection Cable	Multi-conductor cable assembly connecting the Upper Adhesive Electrode Patch to the Monitoring and Defibrillation Unit with Lower Adhesive Electrode Patch.

Figure 3.2: Schematic of the Jewel (ES-2) System Components

Jewel Accessories (ES-1, ES-2)

The Jewel System is packaged with accessories to aid in the application and removal of the Jewel System. The Skin Preparation Accessories aid in cleaning the torso area prior to application of the Adhesive Patches. A Placement Accessory ensures the Adhesive Electrode Patches are aligned correctly on the subject's torso. Removal Accessories are provided to aid in removing the Adhesive Electrode Patches and cleaning the skin area.

The Adhesive Electrode Patches are intended to be applied to an adult patient in an anterior-apical monitoring vector configuration. The Upper Adhesive Electrode Patch is applied to the skin above the right pectoral muscle, and the Lower Adhesive Electrode Patch is applied such that the defibrillation pad area is located along the left mid-axillary line. Figure 3.2 is a depiction of the Jewel System applied to a patient.

[figure not shown]

Figure 3.2: Jewel (ES-1, ES-2) System Applied to a Patient's Torso

The MADIT-RIT study results demonstrated a reduction in inappropriate therapy and all-cause mortality when ICDs were programmed to deliver therapy for tachyarrhythmias of 200 bpm and higher.⁴ The Jewel System algorithm was designed with the MADIT-RIT rate cut-off as a guide for determining if a rhythm is life-threatening and requires therapy. The Jewel System does not allow the physician to program the device to alternate heart rate detection thresholds.

The Jewel System monitors a patient's ECG through five (5) electrodes located on the Adhesive Electrode Patches. The Jewel System employs a proprietary algorithm to detect and classify fast VT or VF that is deemed to be life-threatening ("shockable") versus cardiac rhythms that are non-life threatening ("non-shockable"). In the event of a shockable rhythm, the Jewel System firmware initiates the charge cycle of the capacitors, and in parallel, the Jewel System will initiate an alarm sequence to alert the patient that the device is preparing to deliver a shock. If the patient is conscious, the patient is instructed to press the Control Buttons to stop the alarms and prevent the delivery of the shock. If the patient does not respond, and the shockable rhythm continues, the Jewel System will continue to alarm the patient and also give a verbal warning to bystanders that a shock will be delivered. The Jewel System delivers the initial therapeutic shock with a fixed energy of approximately 150 joules using a biphasic truncated exponential defibrillation waveform using a constant energy pulse that is adjusted based on the transthoracic impedance (TTI) of the patient at the time of therapy delivery. Using a cardioversion algorithm, the Jewel System will attempt to cardiovert the rhythm and synchronize the shock with the R-peak of the QRS complex. This automatic synchronization delivers a cardioversion shock to a patient if R-peaks are detected, suggesting that the

⁴ Moss AJ, Schuger C, Beck CA, et al. Reduction in inappropriate therapy and mortality through ICD programming. *N Engl J Med* 2012;367:2275-83. DOI: 10.1056/NEJMoa1211107

rhythm is a life-threatening VT. If the cardioversion algorithm is not able to identify a regular R-peak during the ventricular arrhythmia, the Jewel System will deliver an asynchronous defibrillation shock. After the initial shock of approximately 150 joules, if the Jewel System continues to detect a shockable rhythm, the Jewel System will re-initiate the alarm sequence and continue to deliver a salvo of up to four (4) additional shocks of approximately 162 joules, totaling five (5) consecutive shocks (150, 162, 162, 162, 162 joules).

The Jewel System is a Class III medical device in the United States and a Class IIb medical device in the European Union (EU).

3.3. DEVICE DESCRIPTION: JEWEL EP LAB SYSTEM

The Jewel EP Lab System delivers the same biphasic truncated exponential waveform as the Jewel System. The waveform parameters utilized by the Jewel EP Lab System are similar to other commercially-approved external defibrillators.

The Jewel EP Lab System consists of a Jewel System modified with the addition of a Controller Box. The Controller Box allows the operator to manually charge the Jewel System capacitors as well as manually administer a defibrillation shock. This minimizes the safety risk to the patient by limiting the VT or VF to a relatively short time period (less than 20-30 seconds).

The Control Buttons on the Controller Box which allow the clinicians to charge the capacitors and deliver the shock are unique to the Jewel EP Lab System. Since the user will control the timing of the shock delivery using the Controller Box, the shock will not be automatically synchronized to the R-peak of the ECG complex using the cardioversion algorithm that is integrated into the Jewel System. Since the shock is not controlled by the Jewel System, the TTI measurement used to determine the energy waveform is taken within 1 second of when the capacitors are fully charged.

Additionally, the Jewel EP Lab System contains a lower strength hydrocolloid adhesive in the Upper and Lower Adhesive Electrode Patches. The reduced peel strength of the hydrocolloid adhesive allows for easy peel-off of the Adhesive Electrode Patches after the short-term wear duration in the EP lab procedure. The regular strength hydrocolloid adhesive used in the Jewel System is only located in non-defibrillation areas to allow for an 8 day wear duration. Following the same geometry, the Jewel EP Lab System hydrocolloid does not cover any part of the ECG sensing or defibrillation electrodes, and therefore will not have any impact on the defibrillation area during the procedure.

The Jewel EP Lab System Instructions for Use contains a thorough description of the product's preparation and administration procedures.

The ES-2 model of the Jewel EP Lab System will be used as the study device for new subjects enrolled in the Jewel EP Lab Study.

3.4. PRIOR CLINICAL EXPERIENCE WITH THE JEWEL AND JEWEL EP LAB SYSTEMS

The Jewel System and the Jewel EP Lab System have both been investigated in animal models to characterize the safety of external defibrillation therapy. In addition, the full array of relevant biocompatibility tests were performed in accordance with ISO 10993. A complete summary of preclinical information regarding the Jewel EP Lab System is available in the Investigator's Brochure.

3.5. RISKS AND BENEFITS OF THE JEWEL EP LAB SYSTEM

The Jewel EP Lab System will be used for investigational purposes only. It is not intended for commercial use. The study device will be used for external defibrillation during a standard EP procedure. A detailed Risk Analysis has been completed and the risk to benefit ratio has been determined to be acceptable for use in a clinical investigational study.

4. STUDY OBJECTIVE

The primary objective of this study is to demonstrate safety and clinical effectiveness of the Jewel EP Lab System, utilizing either the ES-1 or the ES-2 model of the Jewel EP Lab System. The Jewel EP Lab System will be used to deliver a single transthoracic defibrillation shock to terminate life-threatening VT or VF to patients undergoing a cardiac EP procedure.

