Similar to the ZOLL LifeVest and AEDs, the Jewel System is designed to deliver a fixed energy of approximately 150 joules using a biphasic truncated exponential waveform that is adjusted based on the transthoracic impedance of the patient. The purpose of this clinical study is to demonstrate the safety and effectiveness of the Jewel EP Lab System to deliver a single transthoracic defibrillation shock to terminate life-threatening VT or VF.

The study is planned to be conducted in standard clinical cases, such as an EP study or an ablation case, in which life-threatening VT or VF may spontaneously occur or be induced. As with similar EP lab studies, the duration of life-threatening VT or VF will be limited to a relatively short time period (less than 20-30 seconds) to minimize the safety risk to the patient since the duration of life-threatening VT or VF has been shown to be inversely proportional to the success of defibrillation

⁵ American Heart Association. 2005 American Heart Association Guidelines for Cardiopulmonary Resuscitation and Emergency Cardiovascular Care. *Circulation*, Supplement 2005.

⁶ Bain et.al. Multicenter study of principles-based waveforms for external defibrillation. *Annals of Emergency Medicine*, Jan 2011: 37:1, 5-12.

⁷ Auricchio, A. et.al. "Clinical Efficacy of the Wearable Cardioverter-Defibrillator in Acutely Terminating Episodes of Ventricular Fibrillation." *Amer J Cardiol*. 1998; 81: 1253-1256.

therapy.^{8,9} Unlike the Jewel EP Lab System, the Jewel System is designed for ambulatory patients and therefore if the system detects a shockable rhythm, the firmware initiates the alarm sequence, allowing a conscious patient to have time to respond and press the Control Buttons to prevent delivery of a shock (approximately 50-60 seconds from the initial detection of the shockable rhythm). Although this is acceptable for an out-of-hospital event, the Jewel EP Lab System is a derivative of the Jewel System designed for the EP lab environment to allow the clinical user to manually charge the capacitors and trigger the delivery of the defibrillation shock at any time during the procedure. The Jewel EP Lab System does not require waiting for the algorithm to detect and classify a shockable rhythm. This ensures that the clinical user has full control of the delivery and timing of the therapeutic shock in order to avoid a prolongation of the response time during the acute EP lab procedure.

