6.2. PRIMARY SAFETY ENDPOINT

Descriptive statistics of safety outcomes will be reported to ensure that device safety performance is clinically meaningful. All adverse events observed during the acute procedure will be tabulated and presented along with the duration, severity, and relatedness to the Jewel EP Lab System. The proportion of subjects experiencing an AE or SAE will also be presented. No formal safety analyses will be performed due to the fact that the sample size does not allow for a powered safety endpoint.

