7. STUDY POPULATION

7.1. PATIENT INCLUSION/EXCLUSION CRITERIA

The study will only enroll up to 24 subjects that fulfill the eligibility criteria of the investigation. Subject participation is voluntary and the study will be conducted in accordance with the Declaration of Helsinki.

Inclusion Criteria:

Candidates for this study must meet all the following criteria:

- 1) Subjects of both genders of at least 18 years of age.
- 2) Subjects who are scheduled for a standard EP clinical procedure where life-threatening VT or VF may spontaneously occur or may be induced.

Exclusion Criteria:

Candidates will be ineligible for enrollment if any of the following conditions apply:

- 1) Subjects who may require sterile access to the right upper pectoral or lower left torso regions during the planned EP procedure.
- 2) Subjects who have taken amiodarone in the past 3 months.
- 3) Subjects with an existing unipolar pacemaker.
- 4) Subjects who exhibit a left ventricular ejection fraction (LVEF) less than 20% (as assessed by techniques such as echocardiography, magnetic resonance imaging, or radionuclide angiography within the last 6 months).
- 5) Subjects who have been diagnosed with heart failure (Class IV) or experienced an acute heart failure exacerbation within the previous 30 days.
- 6) Subjects who exhibit unstable angina.
- 7) Subjects with atrial fibrillation with contraindication to anticoagulation or improper anticoagulation management.
- 8) Subjects who are participating in an investigational study of a drug, biologic, or device not currently approved for marketing.
- 9) Subjects who are allergic to or have had a known adverse reaction to medical adhesives.
- 10) Subjects who have active skin breakdown, erythema, or other signs of infection in the pectoral or torso regions where the study device is applied.
- 11) Subjects with a lower abdomen circumference of less than 68.5 cm or greater than 142 cm.
- 12) Females who are pregnant or breastfeeding, or planning to be pregnant in the next 12 months.
- 13) Subjects who cannot provide or have diminished capacity to provide informed consent.
- 14) Any condition that an Investigator believes would interfere with the intent of the study or is not in the best interest of the patient.
- 15) Any patient that according to the Declaration of Helsinki is unsuitable for enrollment.

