In cases where the patient is stable, the VT/VF may be allowed to continue for 20-30 seconds to ensure the algorithm has sufficient ECG data to make a rhythm determination over multiple eight-second segments. The timing of the defibrillation shock is under the discretion of the physician to ensure patient safety. In the case where VT/VF is not sustained for the minimum of 8-12 seconds, the indicator light on the Controller Box will not illuminate. The ECG data recorded on the Jewel EP Lab System will also be analyzed post-procedure to assess the performance of the algorithm.

In the event that the defibrillation shock delivered through the Jewel EP Lab System does not successfully terminate the VT/VF, the rescue defibrillator will be used to deliver subsequent defibrillation shock(s).

Throughout the clinical procedure, the Jewel EP Lab System will only be used in appropriate cases based on physician judgment.

- In the case that a defibrillation shock is delivered through the Jewel EP Lab System, the clinical procedure will continue as planned. If a subsequent defibrillation shock is required during the procedure, the rescue defibrillator will be used. The Jewel EP Lab System will only be employed for a single shock during each procedure. In the case that the Jewel EP Lab System is used to deliver a defibrillation shock and the subject meets all enrollment criteria, the subject will be included in the treatment analysis for the primary endpoint.
- In the case that the Jewel EP Lab System is not used to deliver a defibrillation shock during the procedure, the subject will not be included in the treatment analysis to meet the sample size requirements per the statistical plan. In approximately 30 percent of cases, life-threatening VT or VF may not occur or be inducible and therefore an external defibrillation shock would not be required.¹¹ In addition, based on physician judgment, the Jewel EP Lab System may not be used to provide a defibrillation shock during the procedure. In these cases, the subject will not be included in the treatment analysis for the primary endpoint, however, an Intent-to-Treat (ITT) analysis will be performed for informational purpose.

At the conclusion of the acute procedure, the Jewel EP Lab System will be removed from the subject and the Controller Box will be disconnected from the Adhesive Electrode Patches. The subject will exit the study immediately after completion of the EP clinical procedure.

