For the calculation of sample size, this study will use an anticipated first shock conversion success rate of 87.5% in the EP Lab Study with a performance goal of 62%, the same as the first shock success rate seen in VEST. The performance of the Jewel will be considered acceptable if the lower confidence limit exceeds the performance goal of 62% (green line in the graph on page 24).

The sample size for this study is a maximum of 24 subjects. Subjects can be treated with either the ES-1 or the ES-2 model of the Jewel EP Lab System, as the devices are representative of each other. This sample size is based on a group sequential design measuring the observed proportion of successful life-threatening VT or VF terminations. The group sequential design uses a Pocock alpha spending function and allows for testing after 12, 18, and 24 subjects are enrolled. The design controls the overall Type I error rate at 5%. In line with the Pocock alpha spending function, a one-sided lower 97.4% exact confidence bound will be calculated using the exact binomial (Clopper-Pearson) method at each testing point.

Primary Endpoint Analysis:

Upon completion of the Jewel EP Lab Study, all clinical data from both the ES-1 and ES-2 models of the Jewel EP Lab System will be pooled, as the devices are representative of each other. The primary endpoint will evaluate the percent of successful terminations of life-threatening VT or VF in subjects who are in subjects who are enrolled in compliance with the protocol-defined entry criteria and treated with the Jewel EP Lab System (either ES-1 or ES-2 model).

Using the VEST RCT results for the first shock success as a guide, the performance goal of 62% was established for the Jewel EP Lab Study. The endpoint will be achieved if the lower confidence limit exceeds the performance goal of 62% using a one-sided lower 94.5% exact confidence bound at one of the three testing points.

These conditions ensure that performance will be in line with previously published randomized controlled trial results on a relevant comparator, the ZOLL LifeVest which, is the only commercially approved WCD in Europe or the US. The method for testing the conversion success will follow these steps:

1. If after attempting to convert the first 12 subjects, all subjects have been successfully converted (100% conversion rate) the trial will be stopped and deemed a success. Otherwise, continue to Step 2.

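### Demonstrating safety is part of the stated objective, but the plan treats safety descriptively and sets no criterion by which that part could be met

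*Combined protocol and SAP*

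**What the plan says.** **Objective and purpose.** Section 4 reads: "The primary objective of this study is to demonstrate safety and clinical effectiveness of the Jewel EP Lab System". The synopsis gives the same primary objective. Section 5 says: "The purpose of this clinical study is to demonstrate the safety and effectiveness of the Jewel EP Lab System".

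**Safety analysis.** Section 6.2, whose heading calls it the primary safety endpoint, says: "Descriptive statistics of safety outcomes will be reported to ensure that device safety performance is clinically meaningful". It plans a tabulation of events with duration, severity and relatedness, and the proportion of subjects with an AE or SAE. It then says: "No formal safety analyses will be performed due to the fact that the sample size does not allow for a powered safety endpoint". The synopsis carries the same text under a plain safety-endpoint label. Neither place gives a safety hypothesis, an acceptable event rate or a confidence interval.

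**Size and stopping.** Section 7.1 says: "The study will only enroll up to 24 subjects that fulfill the eligibility criteria of the investigation". Section 11.1 describes a design that "allows for testing after 12, 18, and 24 subjects are enrolled". At the first look, if "all subjects have been successfully converted (100% conversion rate) the trial will be stopped and deemed a success". The only other numeric stop, more than three failures, also counts conversions.

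**Who is counted.** Section 8.2 expects that "In approximately 30 percent of cases, life-threatening VT or VF may not occur or be inducible". Section 9 keeps every enrolled subject, shocked or not, in the reporting of results. Under Section 8.3, observation ends with the procedure unless an adverse event was seen during it.

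**The concern.** One objective has two halves held to different standards. Effectiveness has a 62% performance goal, exact confidence bounds, a 5% overall Type I error rate and three testing points. Safety has a table. A tabulation with no threshold can describe what happened. It cannot demonstrate safety, nor can it ensure that safety performance reaches any given level, as Section 6.2 says it will.

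What is at stake is the conclusion the final report may draw. A clean safety table from 12 to 24 shocked subjects, set beside an objective to demonstrate safety, invites a claim the data cannot carry. With no interval specified, nothing in the planned output would show the reader how much remains uncertain.

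**Working it through.** **1. The plan's own figure.** The documents give no safety figure, but the exact bound for 12/12 conversions in Section 11.1 is the mirror image of the bound for 0/12 events. The one-sided 97.4% lower limit for n/n successes is 0.026^(1/n). At n = 12 this is 0.738, against about 73.7% in the plan. The mirrored upper limit for 0/12 events is 1 − 0.738 = 26.2%. The plan's other exact bounds also reproduce to within rounding: 72.9% (17/18), 65.5% (16/18) and 67.8% (21/24), against 72.8%, 65.4% and 67.8%.

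**2. Shock-related events.** These can occur only in shocked subjects. The denominators are the three testing points in Section 11.1, read as shocked subjects because its first step counts subjects in whom conversion was attempted. The exact one-sided 95% upper limit with zero events is 1 − 0.05^(1/n).

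| Shocked n | Limit, 0 events | Limit, 1 event |
|---|---|---|
| 12 | 22.1% | 33.9% |
| 18 | 15.3% | 23.8% |
| 24 | 11.7% | 18.3% |

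The one-event column is the Clopper-Pearson limit, the 0.95 quantile of Beta(2, n − 1).

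**3. Events possible in anyone fitted with the device.** The denominator is larger, and it depends on what 24 counts. Assume 30% are not shocked (Section 8.2).

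- If the testing points count shocked subjects, 12/0.7 = 17.1 and 24/0.7 = 34.3, so about 17 and 34 are fitted. The zero-event limits are 1 − 0.05^(1/17) = 16.2% and 1 − 0.05^(1/34) = 8.4%.
- If 24 caps enrolment, as Section 7.1 can be read, the limit at 24 fitted is 11.7%. About 24 × 0.7 = 16.8, or 17, would be shocked, and the limit for shock-related events would be 16.2%.

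**4. Chance of seeing no event at all.** The documents give no acceptable rate, so a true rate of 5% is used here only as an illustration. The chance is 0.95^n.

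| n | Chance of no event at a true 5% rate |
|---|---|
| 12 | 54% |
| 17 | 42% |
| 24 | 29% |
| 34 | 17% |

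**5. Scale.** The smallest n at which zero events excludes a rate q at one-sided 95% is ln(0.05)/ln(1 − q), rounded up. That is 29 for 10%, 59 for 5% and 299 for 1%. These three rates are also assumptions.

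**The case against.** **Disclosure.** The strongest reply is that the plan hides nothing. The synopsis and Section 6.2 both say safety is descriptive and unpowered. Section 6 calls this a feasibility study. The synopsis reserves the word primary, among endpoints, for effectiveness. All of this stands, and it limits the weight of the point. It does not remove the mismatch, because the objective and purpose statements still promise a demonstration. The feasibility label supports describing acute safety rather than demonstrating it.

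**A false safety claim at the first look.** A reader might infer that a stop at 12/12 conversions would formally declare safety demonstrated. The documents do not say so. The success rule in Section 11.1 concerns conversion only, and no safety decision is attached to it. For the same reason, it goes too far to say the safety objective has been shown to be unattainable. With no criterion there is nothing to pass or fail.

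**Rates above 20% for any adverse event.** A reader might also apply the 22.1% limit to all adverse events. It applies only to shock-related events in 12 shocked subjects. Section 9 keeps all enrolled subjects in the reporting, and on that base the limit is lower (step 3 of the working).

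**No interval.** Descriptive statistics do not exclude confidence intervals. The accurate statement is that the plan specifies none.

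**Conclusion.** The point holds as a mismatch between the stated objective and the planned analysis. The documents commit to demonstrating safety in three places, plan description only, and set no criterion by which the commitment could be judged.

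Even with no events, the trial would leave shock-related rates of up to 11.7% to 22.1% compatible with the data, depending on where it stops. For events in anyone fitted with the device, the range is about 8.4% to 16.2%. These ranges assume that the testing points count shocked subjects; the second also assumes 30% non-use. Reading 24 as an enrolment cap changes the figures (11.7% at 24 fitted) but not the conclusion. Whether such limits are acceptable is a judgement, because the documents name no benchmark.

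Severity is minor to moderate. The limit is disclosed, and neither the effectiveness test nor its error rate is affected.

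**What to change.** - In the synopsis and Sections 4 and 5, restate the objective and purpose as demonstrating effectiveness and describing acute procedural safety.
- Retitle Section 6.2, and its contents entry, as a descriptive safety endpoint. Reword its opening sentence so that it no longer says descriptive statistics will ensure a level of safety.
- In Section 6.2 and the synopsis safety row, add exact (Clopper-Pearson) one-sided 95% upper limits to the AE and SAE proportions. Use two stated denominators: all subjects fitted with the device, and shocked subjects for shock-related events.
- State whether 24 counts enrolled or shocked subjects, so that both denominators are clear.

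The cost is wording and a few extra entries in the safety table. No additional subjects, procedures or alpha are needed. The downside for the sponsor is a weaker safety claim.
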